3.4.5 Secondary Endpoints - Safety

The occurrences of laboratory-confirmed symptomatic COVID-19 and serologically-confirmed SARS-CoV-2 infection will be described by percentages of participants with infection during the analysis period with 95% CI by Clopper-Pearson methods.

Participants with active SARS-CoV-2 infection at baseline (as determined by positive NAAT at D01) will be listed separately, if applicable.

If the total number of observed COVID-19 clinical illness cases collected during the analysis period is less than 5 in all groups, no summary analysis will be performed, and a listing of observed cases will be provided.

For Supplemental Cohorts Comparator group, laboratory-confirmed symptomatic COVID-19 and serologically-confirmed SARS-CoV-2 infection that occurred after authorized/approved COVID-19 vaccine injection will be listed separately.

For Supplemental Cohort 1 and Cohort 2 booster arms, laboratory-confirmed symptomatic COVID-19 and serologically-confirmed SARS-CoV-2 infection that occurred after authorized/approved COVID-19 vaccine injection during the study period will be listed separately.

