3.4.3 Primary Endpoints - Safety

The main parameter will be described for all safety endpoints. The percentage of participants (using as denominator the number of participants) will be provided for analysis of solicited AEs, unsolicited AEs (including immediate systemic AEs within 30 minutes), SAEs, AESIs and MAAEs. The corresponding 95% CIs for the percentages will be calculated based on the Clopper--Pearson method. In the priming vaccine groups (comparator for Cohorts 1 and 2), subgroup analyses will be performed by age group (18-55 years and ≥ 56 years), high-risk medical conditions group, and baseline SARS-CoV-2 Naïve status for main safety analyses. In the booster vaccine groups (in Cohorts 1 and 2), subgroup analyses will be performed by age group (18-55 years and ≥ 56 years), high-risk medical conditions group, priming vaccine platform and individual priming vaccine. Safety endpoints will be analyzed for each of the CoV2 preS dTM primary series dosage administered in the original Phase II cohort (ie, 5-10-15 μ g) for Cohort 2.

Safety endpoints that occurred after authorized/approved COVID-19 vaccine injection will be listed separately.

SafAS population will be used for safety analyses for the following endpoints:

- Presence, and relationship of unsolicited (immediate) systemic AEs reported in the 30 minutes after each vaccination.
- Presence, time of onset, number of days of occurrence, intensity, action taken, and whether the reaction led to early termination from the study, of solicited (pre-listed in the participant's DC and CRF) injection site reactions and systemic reactions occurring up to 7 days after each vaccination.
- Presence, nature (Medical Dictionary for Regulatory Activities [MedDRA] system organ class [SOC] and preferred term [PT]), time of onset, duration, intensity, relationship to

vaccination and whether the event led to early termination from the study of unsolicited AEs reported up to 21 days after the last vaccination.

- Presence, nature (MedDRA SOC and PT), time of onset, seriousness criteria, relationship to vaccination, outcome, and whether the event led to early termination from the study, of SAEs.
- Presence, seriousness, intensity, nature (MedDRA SOC and PT), time of onset, duration, relationship to vaccination of all protocol-specified AESIs from the time of the first study vaccination throughout the study.

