4.2 Complementary Information on Derived Endpoints: Calculation Methods

4.2.1 Safety

Main analysis, sensitivity analysis and complementary analysis will be undertaken based on safety analysis set. Main safety analysis will be performed as the key safety results, sensitivity and complementary analysis will be performed as supportive results. The rationale for conducting the sensitivity and complementary analysis is because of the high likelihood for participants in the study to receive a non-study authorized/approved COVID-19 vaccine for Supplemental Cohorts Comparator group, and for Supplemental Cohort 1 and Cohort 2 booster arms, in case the participants receive a non-study authorized/approval COVID-19 vaccine after booster dose. These study participants will be allowed to continue study participation if they choose to do so; while continuation in the study will include all study procedures including safety follow-up and therefore safety data will be collected after receipt of a non-study authorized/approved COVID-19 vaccine which will interfere with interpretation of the safety data following study vaccination.

Main analysis will be applied for all safety endpoints. It includes all adverse events or reactions with time of onset before the date of receiving a non-study authorized/approved COVID-19 vaccine (if applicable) during study period. For some selected endpoints, main analysis will only include safety data collected before the date of receiving a non-study authorized/approved COVID-19 vaccine (censored by the date) corresponding to those adverse events or reactions included. For the other endpoints, safety analysis will include all data collected in the entire collection period corresponding to those adverse events or reactions. Details of conducting main analysis for those endpoints including censored data are further clarified in the following subsections.

Sensitivity analysis will be conducted for some selected endpoints. It includes all adverse events or reactions with time of onset before receiving a non-study authorized/approved COVID-19 vaccine during the study period and includes safety data collected over the entire collection period corresponding to those adverse events or reactions. Details of conducting sensitivity analysis for those specific endpoints are further clarified in the following subsections.

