4.2.2 Other Safety Endpoints

For the safety endpoint related to SARS-CoV-2 infections (endpoints from [Section 4.2.2.1](#) to [Section 4.2.2.7](#)), main analysis will be applied including only those cases with start date before a participant received a non-study authorized/approved COVID-19 vaccine if applicable. Other cases with start date reported in participants after the receipt of an authorized/approved COVID-19 vaccine will be listed separately.

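### Long-window SAE, AESI, MAAE and COVID-19 percentages drop events after a non-study vaccine but keep the participants in the denominator, so they understate risk over the period they are labelled with

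*SAP*

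**What the plan says.** - **COVID-19 endpoints.** Section 3.4.5 summarises them as "described by percentages of participants with infection during the analysis period with 95% CI by Clopper-Pearson methods". The sentence names no denominator. Section 4.2.2 adds that "main analysis will be applied including only those cases with start date before a participant received a non-study authorized/approved COVID-19 vaccine if applicable". For the Comparator Group, section 3.4.5 says that "infection that occurred after authorized/approved COVID-19 vaccine injection will be listed separately", and the booster arms have a parallel sentence.
- **Adverse events.** Section 3.4.3 is explicit about the denominator: "The percentage of participants (using as denominator the number of participants) will be provided for analysis of solicited AEs, unsolicited AEs", and the same sentence goes on to SAEs, AESIs and MAAEs. Section 4.2.1 defines the main analysis: "It includes all adverse events or reactions with time of onset before the date of receiving a non-study authorized/approved COVID-19 vaccine".
- **Periods.** Sections 4.2.1.2.6 to 4.2.1.2.8 tabulate MAAEs, SAEs and AESIs for a 21-day post-dose period, a 6-month period and the entire study. The entire-study line is glossed as covering all such events during the study. Planned participation is about 366 days in the booster arms and about 386 days in the Comparator Group.
- **Expected uptake.** Section 4.2.1 refers to a "high likelihood for participants in the study to receive a non-study authorized/approved COVID-19 vaccine for Supplemental Cohorts Comparator group". For the booster arms it speaks only of the case that it happens.

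**The concern.** A Comparator participant who is vaccinated outside the study at month 3 can contribute an event only in those three months, yet is counted as one full participant in a table labelled as covering the whole study. That person is in effect a twelve-month non-event. A binomial percentage with a Clopper-Pearson interval then estimates neither the risk over the labelled period nor the risk while free of non-study vaccine.

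Table 2.1 lists SAEs, AESIs and MAAEs throughout the study as primary safety endpoints and COVID-19 occurrences as the secondary safety endpoint. At stake is whether these headline frequencies describe what their labels say. If the cut-off bites harder in one group than another, part of any difference in the displayed percentages will be an artefact of shorter observation.

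**Working it through.** The SAP gives no expected event count, event risk or uptake rate for these endpoints, so there is no stated figure to reproduce. The calculation below is illustrative.

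**Inputs from the SAP.** Follow-up F = 386 days (Comparator) and 366 days (booster); 515 planned Comparators.

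**Assumptions, not in the SAP.** Twelve-month risk 10% with the same constant hazard in every arm, so λ = −ln(0.9)/365 = 0.0002887 per day. Booster uptake of non-study vaccine 10%. Comparator uptake u from 0 to 70%. Vaccination dates uniform from day 43 either to the end of follow-up or to day 180.

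**Formula.** With vaccination uniform on days a to b:

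crude % = (1 − u)·(1 − e^(−λF)) + u·[1 − (e^(−λa) − e^(−λb)) / (λ(b − a))]

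- Risk over full follow-up: 10.54% at 386 days, 10.03% at 366 days.
- Mean risk up to non-study vaccination: 5.97% (Comparator, D43–D386), 5.70% (booster, D43–D366), 3.16% (either group, D43–D180).

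**At 50% Comparator uptake.**
- Spread over follow-up: Comparator 0.5 × 10.54 + 0.5 × 5.97 = 8.3%; booster 0.9 × 10.03 + 0.1 × 5.70 = 9.6%; ratio 0.86.
- Early (D43–D180): Comparator 0.5 × 10.54 + 0.5 × 3.16 = 6.9%; booster 0.9 × 10.03 + 0.1 × 3.16 = 9.3%; ratio 0.73.

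| Comparator uptake | Spread: Comparator % | Ratio to booster 9.6% | Early: Comparator % | Ratio to booster 9.3% |
|---|---|---|---|---|
| 0% | 10.5 | 1.10 | 10.5 | 1.13 |
| 10% | 10.1 | 1.05 | 9.8 | 1.05 |
| 30% | 9.2 | 0.96 | 8.3 | 0.89 |
| 50% | 8.3 | 0.86 | 6.9 | 0.73 |
| 70% | 7.3 | 0.77 | 5.4 | 0.58 |

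The ratios hardly change at 5% or 20% risk. The interval does not rescue the estimate. In the early-uptake case at 50%, about 35 of 515 Comparators would have a counted event, with Clopper-Pearson limits 4.8% to 9.3%. These exclude the 10.5% that full follow-up would give.

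**Do existing provisions correct it?**
- The sensitivity analysis in section 4.2.1 admits the same events (onset before the non-study vaccine) and only extends the data collected on them.
- The complementary analysis tabulates later AEs separately, in general only if more than 15 subjects are included. It leaves the main percentage alone.
- Later COVID-19 cases are only listed.
- Section 4.2.4.6 derives a follow-up duration that stops at non-study vaccination, but no stated analysis uses it as a denominator.

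**Would a person-time rate alone be enough?** Under a constant hazard it gives 0.105 per person-year in both groups whatever the uptake. It fails if risk is front-loaded. Take 5% risk in months 0–2 and 5% in months 2–12, with 70% of Comparators cut at month 2 and depletion ignored. The booster rate is 0.10/12 = 0.0083 per month. The Comparator rate is (0.05 + 0.3 × 0.05)/(0.3 × 12 + 0.7 × 2) = 0.065/5 = 0.013, which is 1.56 times higher with identical hazards.

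**The case against.** The safety objectives are descriptive. No safety hypothesis or between-group contrast is specified. The Comparator Group is open-label, non-randomised, naïve and aged 18–55 only, while the booster arms are previously vaccinated and include older adults. These groups could not be compared causally even with equal follow-up. The 21-day tables are barely affected, and the listings, the complementary tables and the derived follow-up duration at least make the truncation visible. Section 3.4.5 does not state its denominator, so for COVID-19 the use of all participants is an inference from plain percentages and the absence of any alternative.

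All of that stands, and it limits the weight of the point. It does not remove it: a descriptive percentage must still describe its labelled period, and the understatement arises within each arm without any comparison.

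A reader might go further and infer that the Comparator Group is bound to look artificially safe. The SAP does not support that as a fact. It gives no uptake rates, and at equal 10% uptake the Comparator looks slightly worse (ratio 1.05) because its planned follow-up is 20 days longer. The direction reverses only when Comparator uptake clearly exceeds booster uptake. Nor should the size be judged from an extreme contrast, such as half of Comparators vaccinated at exactly month 3 and no booster participant ever. That would give 6.3% against 10%, but the SAP itself provides for non-study vaccination in the booster arms.

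**Conclusion.** The point holds within limits. The 6-month and entire-study percentages for SAEs, AESIs, MAAEs and COVID-19 understate risk over the labelled period in every arm with non-study vaccination, and no planned analysis corrects this. The understatement is larger in the Comparator Group if its uptake clearly exceeds that of the booster arms, as the SAP expects. The true size cannot be known from the document. At 50% against 10% uptake the illustrated entire-study ratio is 0.86 to 0.73 in place of about 1.05, which is what the longer Comparator follow-up alone would give (10.54/10.03). Those figures rest on the assumed 10% risk, equal constant hazards and the two uptake patterns. No formal test is affected, and the short windows can stay as they are.

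**What to change.** For COVID-19 endpoints, and for SAEs, AESIs and MAAEs in the 6-month and entire-study periods:

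1. Keep the planned percentages. Add cumulative incidence with 95% CI by Kaplan-Meier, or by Aalen-Johansen with death as a competing event, censored at the earliest of non-study vaccine, termination or data cut-off. This should cover the long-window AE tables as well as COVID-19, because a rate alone can mislead when risk is front-loaded.
2. Add exposure-adjusted incidence per 100 person-years with exact Poisson 95% CI as a supporting summary.
3. Define time at risk as the earliest of first event, non-study vaccine, termination, death or data cut-off, minus the V01 date. The section 4.2.4.6 duration cannot be reused: it does not stop at the event, and without other vaccination it takes the maximum of the lock, termination and death dates, which credits time after a participant has left or died.
4. State the denominator in section 3.4.5, and label the main entire-study tables as events before non-study vaccination.

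The cost is modest: a time-to-first-event variable for each endpoint and some added table columns, with no planned output removed. Both added summaries still assume that non-study vaccination is non-informative for the event, and neither makes the non-randomised groups comparable.

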3.4.6 Exploratory Endpoints

Cellular immune response/Mucosal antibody response

Data of each B-cell response and T-cell response will be summarized in GMT with 95% CI using the same method stated in [Section 3.4.4](#). CMIAS population will be applied.

Neutralizing antibody response to emergent SARS-CoV-2 variant strains

Exploratory immunogenicity analysis will be performed by SARS-CoV-2 Pseudovirus Neutralization Assays at NEXELIS testing variants (eg, B.1.1.7, P.1, B.1.617, etc.). The same analysis methods stated in [Section 3.4.4](#) will be applied. GMT, GMTR, proportion of participants having 2FR, 4FR and proportion of responders based on neutralizing antibodies will be analyzed for each SARS-CoV-2 variant strain on each time point respectively.

Details of assay information and corresponding analysis performed are listed in [Appendix A](#).

The neutralizing antibody response to SARS-CoV-2 variant strains (D614G, B.1.351, B.1.1.7, P.1, B.1.617, etc) will be evaluated by country as exploratory purpose.

3.4.7 Handling of Missing Data and Outliers

3.4.7.1 Safety

Generally, no replacement will be done. However, imputations may be done for a limited number of scenarios, some of which are described in this section.

3.4.7.1.1 Immediate

Unsolicited systemic AEs with a missing response to the “Immediate” field will be assumed to have occurred within the 30-minute surveillance period.

3.4.7.1.2 Causal Relationship

By convention, all events reported at the injection site (either solicited or unsolicited) will be considered as related to the administered product and then referred to as reactions. In a same way, all solicited systemic events pre-listed in the CRF are also considered as related to vaccination and will be considered as reactions.

- For unsolicited systemic AE, missing relationship will be considered as related to study vaccine at the time of analysis.
- The missing relationship to study procedures for SAEs will not be imputed.

3.4.7.1.3 Intensity

For solicited reactions, missing intensities will be handled as described in [Section 4.2.1.1.1](#). For unsolicited non-serious AEs, missing intensities will remain missing and will not be imputed.

3.4.7.1.4 Start Date and End Date

Missing or partially missing start dates or end dates for unsolicited AEs (including SAEs) will remain missing and not be imputed. If the start date is missing or partially missing, the time of onset will be considered to be missing. Nevertheless, unsolicited AEs with missing time of onset will be included in analyses according to the last vaccination (computed according to the [Section 4.2.1.2.3](#)). If either the start date or end date is missing or partially missing, the duration will be considered missing.

Missing or partially missing end dates for ongoing solicited AEs will remain missing and not be imputed.

3.4.7.1.5 Action Taken

Missing actions taken will remain missing and not be imputed.

3.4.7.2 Date of COVID-19 Vaccination History Administration

Missing or partially missing date (day) of last prior non-study COVID-19 vaccine administration for Supplemental Cohort Booster Groups will be imputed as below to calculate the duration prior to on-study booster injection:

- Partially missing on day will be imputed as “01” day;
- Complete missing date or date missing on month will not be imputed and will be treated as missing.

3.4.7.3 Immunogenicity

No imputation of missing values and no search for outlier will be performed. LLOQ and ULOQ management will be performed as described in [Section 4.2.3.1](#).

3.5 Interim Analyses

For Supplemental Cohort 1, an interim analysis will be carried out once the following conditions apply:

- Primary immunogenicity data is available up to D15 and primary safety data is available up to D22 for the booster group in Supplemental Cohort 1
- Primary immunogenicity data is available up to D36 and primary safety data is available up to D43 in the Comparator group for Supplemental Cohorts 1 and 2
- Partial database lock is performed

For Supplemental Cohort 2, an interim analysis may be carried out once the following conditions apply:

- Primary immunogenicity data is available up to D15 and primary safety data is available up to D22 for the booster groups in Supplemental Cohort 2
- Primary immunogenicity data is available up to D36 and primary safety data is available up to D43 in the Comparator group for Supplemental Cohorts 1 and 2
- Partial database lock is performed

For Supplemental Cohort 2, a prespecified independent statistical group who will be unblinded at subject level to generate interim outputs including tables, listings, and figures. The treatment code will be masked from the interim outputs. A group of study members will review the interim outputs unblinded at group level, to perform decision-making. Furthermore, the study team will remain blinded on data collected after date cut-off of the interim analysis.

For Supplemental Cohorts 1 and 2, additional interim analyses may be performed at later timepoints.

4 Complementary Information on Assessment Methods

Study assessments and procedures are detailed in Section 8 of the protocol. This section focuses on complementary/additional information not detailed in the protocol.

4.1 Complementary Information for Endpoints Assessment Methods

Not applicable

4.2 Complementary Information on Derived Endpoints: Calculation Methods

4.2.1 Safety

Main analysis, sensitivity analysis and complementary analysis will be undertaken based on safety analysis set. Main safety analysis will be performed as the key safety results, sensitivity and complementary analysis will be performed as supportive results. The rationale for conducting the sensitivity and complementary analysis is because of the high likelihood for participants in the study to receive a non-study authorized/approved COVID-19 vaccine for Supplemental Cohorts Comparator group, and for Supplemental Cohort 1 and Cohort 2 booster arms, in case the participants receive a non-study authorized/approval COVID-19 vaccine after booster dose. These study participants will be allowed to continue study participation if they choose to do so; while continuation in the study will include all study procedures including safety follow-up and therefore safety data will be collected after receipt of a non-study authorized/approved COVID-19 vaccine which will interfere with interpretation of the safety data following study vaccination.

Main analysis will be applied for all safety endpoints. It includes all adverse events or reactions with time of onset before the date of receiving a non-study authorized/approved COVID-19 vaccine (if applicable) during study period. For some selected endpoints, main analysis will only include safety data collected before the date of receiving a non-study authorized/approved COVID-19 vaccine (censored by the date) corresponding to those adverse events or reactions included. For the other endpoints, safety analysis will include all data collected in the entire collection period corresponding to those adverse events or reactions. Details of conducting main analysis for those endpoints including censored data are further clarified in the following subsections.

Sensitivity analysis will be conducted for some selected endpoints. It includes all adverse events or reactions with time of onset before receiving a non-study authorized/approved COVID-19 vaccine during the study period and includes safety data collected over the entire collection period corresponding to those adverse events or reactions. Details of conducting sensitivity analysis for those specific endpoints are further clarified in the following subsections.

Complementary analysis will be applied for some specific endpoints. It includes the adverse events or reactions with time of onset on or after receipt of a non-study authorized/approved COVID-19 vaccine (if applicable) during the study period and including all the corresponding safety data collected in the collection period. Details of conducting complementary analysis for those endpoints applicable will be clarified in the following subsections.

In general, sensitivity analysis will be conducted if there are at least 15 subjects with different values of the endpoint compared to the corresponding main analysis. Complementary analysis will be conducted if there are more than 15 subjects included in the corresponding analysis.

